1.6. Risk/Benefit

Across all completed Amarin-sponsored studies, the proportion of patients (based on the safety population from the randomized, double-blind periods of the studies) experiencing any adverse events was similar for patients on placebo (light paraffin oil) and patients on AMR101 (57.1% and 57.4% for placebo and AMR101, respectively). The proportion of patients experiencing a serious adverse event (SAE) was also similar for both treatment groups (5.2% and 6.0% for placebo and AMR101, respectively). The safety profile in the open-label extensions was similar to that observed in the double-blind treatment periods. There were no SAEs attributed to AMR101 during the open-label extension periods of the studies.

In summary, AMR101 is very well tolerated at daily doses up to 4 g. The side effects reported by the patients taking AMR101 were generally similar to those reported by the patients taking placebo. Ethyl-EPA is a pro-drug, and is rapidly and completely hydrolyzed to EPA. EPA is a natural substance found universally as a component of all cell membranes. It is classified as an essential fatty acid. Because of the nature of EPA, as an essential component of normal tissue and its part in normal metabolism, human studies have demonstrated that it is safe. See the Investigator's Brochure for more information.

2. STUDY OBJECTIVES

The primary objective is, in patients at LDL-C goal while on statin therapy, with established cardiovascular disease (CVD) or at high risk for CVD, and hypertriglyceridemia (fasting triglycerides, TG, ≥ 200 mg/dL and < 500 mg/dL [≥ 2.26 mmol/L and < 5.64 mmol/L]), to evaluate the effect of 4 g/day AMR101 for preventing the occurrence of a first major cardiovascular event of the composite endpoint that includes:

- Cardiovascular (CV) death,
- Nonfatal myocardial infarction (MI),
- Nonfatal stroke,
- Coronary revascularization,
- Unstable angina determined to be caused by myocardial ischemia by invasive/non-invasive testing and requiring emergent hospitalization.

Refer to Appendix B for cardiovascular event definitions.

The secondary objectives of this study are the following:

The key secondary objective is to evaluate the effect of therapy on the composite of death from CV causes, nonfatal MI, coronary revascularization, unstable angina determined to be caused by myocardial ischemia by invasive/non-invasive testing and requiring emergent hospitalization, nonfatal stroke, or peripheral CVD requiring intervention, angioplasty, bypass surgery, or aneurysm repair.

Other secondary objectives:

- To evaluate the effect of therapy on combinations of each of the key secondary objective clinical events in addition to the following clinical events:
 - Cardiac arrhythmia requiring hospitalization
 - Cardiac arrest
 - Peripheral CVD requiring intervention, angioplasty, bypass surgery, or aneurysm repair
 - Total mortality

The tertiary objectives of this study are the following:

- Evaluate the effect of therapy on the occurrence of a second, third, fourth, and fifth major cardiovascular event (same as the primary composite endpoint but for events occurring after the first event);
- To evaluate the effect of therapy on the primary endpoint in subgroups of patients including:
 - Diabetes mellitus
 - Metabolic syndrome as defined by the NCEP ATP III or future criteria as they may evolve;

- To evaluate the effect of therapy on the individual endpoints of new congestive heart failure (CHF), on new CHF as a primary cause of hospitalization, on transient ischemic attack, on amputation for vascular disease and on carotid revascularization;
- Elective coronary revascularization and emergent coronary revascularization;
- To assess the effects regarding lipids, lipoproteins and inflammatory markers including triglycerides (TG), total cholesterol (TC), low-density lipoprotein cholesterol (LDL-C), high-density lipoprotein cholesterol (HDL-C), non-HDL-C, very low-density lipoprotein cholesterol (VLDL-C), apolipoprotein B (apo B), high sensitivity C-reactive protein (hs-CRP) and high sensitivity troponin (hsTnT), as follows:
 - Assessment of the effect of AMR101 on each marker (on-treatment change of markers)
 - Assessment of the effect of the baseline value of each marker on treatment effects (baseline effect on outcomes)
 - To evaluate the effect of therapy for preventing clinical events, as defined above, among all patients in the study, and in subgroups such as patients with diabetes mellitus and patients with substantial on-treatment changes of any of the markers (on-treatment effect on outcomes).
- To evaluate the effect of therapy on new onset diabetes (See appendix C);
- To explore the effect of AMR101 on weight and waist circumference.

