6.1.2.2. Visit 3 (Day 120; ~4 Months)

Patients will return to the Research Site for Visit 3 on Day 120 ± 10 days.

The following procedures will be performed:

- Perform physical examination
- Obtain weight
- Obtain vital signs (systolic and diastolic blood pressure, heart rate, respiratory rate, and oral body temperature)
- Obtain fasting blood samples for:
 - Chemistry and hematology testing
 - Lipid profile
- Review study drug compliance by unused capsule count; discuss with and counsel patients about compliance if needed
- Administer study drug - Note: Study drug should be taken orally with food following the collection of all fasting blood samples
- Assess and record efficacy events
- Assess for and record adverse events
- Record concomitant medication(s)
- Instruct patient:
 - To bring all study supplies with them to the next visit
 - Not to take study drug on the morning of their next visit
 - To fast for ≥ 10 hours prior to the next visit

6.1.2.3. Visits 4, 5, 6 and 7

At Visit 4: Day 360 ± 10 ; Visit 5: Day 720 ± 10 ; Visit 6: Day 1080 ± 10 ; and Visit 7: Day 1440 ± 10 , the following procedures will be performed:

- Perform physical examination
- Obtain weight

- Obtain vital signs (systolic and diastolic blood pressure, heart rate, respiratory rate, and oral body temperature)
- Measure waist circumference (collected at Visit 5 only)
- Obtain a 12-lead electrocardiogram
- Obtain fasting blood samples for:
 - Chemistry and hematology testing
 - Lipid profile
 - Biomarker assays (collected at Visit 5 only)
 - Archiving (in countries and at sites approved by IRB/IEC and dependent on country regulations)
- Review study drug compliance by unused capsule count; discuss with and counsel patients about compliance if needed
- Administer study drug - Note: Study drug should be taken orally with food following the collection of all fasting blood samples
- Assess and record efficacy events
- Assess for and record adverse events
- Record concomitant medication(s)
- Instruct patient:
 - To bring all study supplies with them to the next visit
 - Not to take study drug on the morning of their next visit
 - To fast for ≥ 10 hours prior to the next visit

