6.1.2.2. Visit 3 (Day 120; ~4 Months)

Patients will return to the Research Site for Visit 3 on Day 120 ± 10 days.

The following procedures will be performed:

- Perform physical examination
- Obtain weight
- Obtain vital signs (systolic and diastolic blood pressure, heart rate, respiratory rate, and body temperature)
- Obtain fasting blood samples for:
 - Chemistry and hematology testing
 - Lipid profile
- Review study drug compliance by unused capsule count; discuss with and counsel patients about compliance if needed
- Administer study drug - Note: Study drug should be taken orally with food following the collection of all fasting blood samples
- Assess and record efficacy events
- Assess for and record adverse events
- Record concomitant medication(s)
- Instruct patient:
 - To bring all study supplies with them to the next visit
 - Not to take study drug on the morning of their next visit
 - To fast for ≥ 10 hours prior to the next visit

6.1.2.3. Visits 4, 5, 6 and 7

At Visit 4: Day 360 ± 10 ; Visit 5: Day 720 ± 10 ; Visit 6: Day 1080 ± 10 ; and Visit 7: Day 1440 ± 10 , the following procedures will be performed:

- Perform physical examination
- Obtain weight
- Obtain vital signs (systolic and diastolic blood pressure, heart rate, respiratory rate, and body temperature)
- Measure waist circumference (collected at Visit 5 only)
- Obtain a 12-lead electrocardiogram
- Obtain fasting blood samples for:
 - Chemistry and hematology testing
 - Lipid profile
 - Biomarker assays (collected at Visit 5 only)
 - Archiving (in countries and at sites approved by IRB/IEC and dependent on country regulations)

- Review study drug compliance by unused capsule count; discuss with and counsel patients about compliance if needed
- Administer study drug - Note: Study drug should be taken orally with food following the collection of all fasting blood samples
- Assess and record efficacy events
- Assess for and record adverse events
- Record concomitant medication(s)
- Instruct patient:
 - To bring all study supplies with them to the next visit
 - Not to take study drug on the morning of their next visit
 - To fast for ≥ 10 hours prior to the next visit

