6.3.1.4. Biomarkers Assays

The biomarker assays include: hs-CRP, Apo B and hsTnT.

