9.2.2. Secondary Efficacy Endpoints

The key secondary efficacy endpoint is:

- The composite of death from CV causes, nonfatal MI, coronary revascularization, unstable angina determined to be caused by myocardial ischemia by invasive/non-invasive testing and requiring emergent hospitalization, nonfatal stroke, or peripheral CVD requiring intervention, angioplasty, bypass surgery, or aneurysm repair.

Other secondary efficacy endpoints are as follows (to be tested in said order):

- The composite of total mortality, nonfatal MI, or nonfatal stroke;
- The composite of death from CV causes, nonfatal MI, coronary revascularization, unstable angina determined to be caused by myocardial ischemia by invasive/non-invasive testing and requiring emergent hospitalization, peripheral CVD requiring intervention, or cardiac arrhythmia requiring hospitalization;
- The composite of death from CV causes, nonfatal MI, coronary revascularization, or unstable angina determined to be caused by myocardial ischemia by invasive/non-invasive testing and requiring emergent hospitalization;
- The composite of death from CV causes or nonfatal MI;
- Total mortality;
- Fatal and nonfatal MI (including silent MI);
- Coronary Revascularization;
- Hospitalization for unstable angina determined to be caused by myocardial ischemia by invasive/non-invasive testing ;
- Fatal and nonfatal stroke.

For the secondary endpoints that count a single event, the first occurrence of this type of event will be counted in each patient. For secondary endpoints that are composites of two or more types of events, the first occurrence of any of the event types included in the composite will be counted in each patient.

9.2.3. Tertiary Efficacy Endpoints:

- The second, third, fourth, and fifth major CV event of the primary composite endpoint. The type of (nonfatal) events may occur in any order.
- Primary endpoint in subset of patients with diabetes mellitus;
- Primary endpoint in subset of patients with metabolic syndrome;
- New CHF, new CHF leading to hospitalization, transient ischemic attack, amputation for CVD and carotid revascularization;
- Elective coronary revascularization and emergent coronary revascularization;
- New onset diabetes;
- Fasting TG, TC, LDL-C, HDL-C, non-HDL-C, VLDL-C, apo B, hs-CRP, and hsTnT: effect of baseline and on-treatment change of biomarkers on primary and key secondary endpoints;

- CV mortality;
- Cardiac Arrhythmias requiring hospitalization;
- Cardiac Arrest;

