12.2.4.4. Tertiary Endpoints

For event rates, the statistical analyses of the tertiary endpoints (see section 9.2.3) will be similar to the analysis of the secondary efficacy endpoints. All tertiary analyses will be conducted for the ITT population. No adjustments for multiple testing will be made.

For measurements of lipids, lipoproteins and inflammatory markers the change from baseline will be analyzed in the units of each marker, and the percent change from baseline. Since these biomarkers are typically not normally distributed, the Wilcoxon rank-sum test will be used for treatment comparisons of the percent change from baseline, and medians and quartiles will be provided for each treatment group. The medians of the differences between the treatment groups and 95% confidence intervals will be estimated with the Hodges-Lehmann method.

New onset diabetes is defined as Type 2 diabetes newly diagnosed during the treatment/follow-up period (i.e. patients with no history of diabetes at randomization, with the test as listed in Appendix C).

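### The tertiary objective compares treatments within subgroups defined by on-treatment marker change, which treatment itself alters, so the comparison is not randomised; for three of nine markers about half of first primary events precede the first on-treatment value

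*Combined protocol and SAP*

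**What the plan says.** **Objective.** Section 2 of the protocol (Amendment 1, repeated in its synopsis and present in the 2011 protocol) lists nine markers: TG, TC, LDL-C, HDL-C, non-HDL-C, VLDL-C, apo B, hs-CRP and hsTnT. One sub-item is to evaluate the effect of therapy on clinical events in subgroups that include "patients with substantial on-treatment changes of any of the markers (on-treatment effect on outcomes").

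**Endpoint.** Section 9.2.3 (Amendment 1) lists, for the same markers, the "effect of baseline and on-treatment change of biomarkers on primary and key secondary endpoints".

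**Method.** Section 12.2.4.4 says that tertiary analyses of event rates "will be similar to the analysis of the secondary efficacy endpoints". Section 12.2.4.3 uses the primary endpoint's log-rank test and a Cox model for those, and Section 12.2.4.2 counts time from randomisation. Marker change is compared between arms by Wilcoxon and Hodges-Lehmann methods. There is no multiplicity adjustment. Section 12.2.4.5 lists no subgroup defined by on-treatment change, but the list is open and the complete one is left to the SAP.

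**Timing.**
- Section 6.3.1.4: "The biomarker assays include: hs-CRP, Apo B and hsTnT". Section 6.1.2.3, covering Visits 4 to 7: "Biomarker assays (collected at Visit 5 only"), with "Visit 5: Day 720 ± 10". The only other scheduled post-baseline sample is at the Last Visit (Section 6.1.2.5, Appendix A).
- Lipid profiles start at Visit 3: "Patients will return to the Research Site for Visit 3 on Day 120" (Section 6.1.2.2).
- Under Section 6.3.1.2, the LDL-C change used in the statistical analysis is ultracentrifugation at Visit 2 and Visit 4 (Day 360).

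**The concern.** A treatment effect within a subgroup is protected by randomisation only if treatment cannot affect membership. Here it can. In the ANCHOR results (2011 protocol, Section 1.3), median TG changed by +5.9% on placebo and by -17.5% on 4 g/day; apo B and hs-CRP also fell relative to placebo. A placebo patient with a large fall and an AMR101 patient with the same fall reached it for different reasons and may differ in underlying risk.

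The timing adds two problems. A patient who dies before the marker visit has no value and cannot be classified. A patient with an earlier nonfatal event can be classified, but the marker was then measured after the outcome it is meant to explain, and the event or its treatment may have changed it. If time still runs from randomisation, both kinds of distortion enter the estimate.

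At stake is whether a difference seen in such a subgroup can be read as an effect of the drug. As the objective is worded, it cannot.

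**Working it through.** **1. Reproduce the plan's event number.** Inputs (Sections 12.2.4.2 and 12.3): hazard ratio 0.85, two-sided alpha 0.0476, power 90%, allocation 1:1.

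Events = 4 × (z for 0.0238 + z for 0.10)² / (ln 0.85)² = 4 × (1.981 + 1.282)² / 0.02641 = 1612. This matches the plan.

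**2. Hazards.** Placebo risk is 23.6% by 4 years (Section 12.3). With a constant hazard, placebo = -ln(1 - 0.236)/4 = 0.0673 per year and AMR101 = 0.85 × 0.0673 = 0.0572 per year.

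**3. Simple four-year share, placebo arm.** Share before day d = [1 - exp(-0.0673 × d/365.25)] / 0.236.
- Day 120: 0.0219/0.236 = 9.3%
- Day 360: 0.0642/0.236 = 27.2%
- Day 720: 0.1242/0.236 = 52.6%

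**4. Trial-wide share, both arms.** Assumptions: uniform 18-month accrual and no dropout. Section 3.4 supports two follow-up ranges: 3.25 to 4.75 years, as stated for individual patients, or 3.5 to 5.0 years, from 3.5 years of follow-up after an 18-month enrolment. The average event probability by study end is 0.2200 or 0.2320. By Days 120, 360 and 720 it is 0.0202, 0.0595 and 0.1154.

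| First value used | Markers | Share (events of 1612), 3.25-4.75 y | Share (events of 1612), 3.5-5.0 y |
|---|---|---|---|
| Day 120 | TG, TC, HDL-C, non-HDL-C, VLDL-C | 9.2% (148) | 8.7% (141) |
| Day 360 | LDL-C by ultracentrifugation | 27.0% (436) | 0.0595/0.2320 = 25.6% (413) |
| Day 720 | apo B, hs-CRP, hsTnT | 52.5% (846) | 49.8% (802) |

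**5. Sensitivity at Day 720.** With follow-up of 3.25 to 4.75 years, varying the placebo rate (5.9% per year as a hazard, 20.8% by 4 years, 5.2% per year as a hazard) gives 51.8% to 52.5%. If the event-driven trial ran a year longer than its stated range (4.25 to 5.75 years, an assumption), the share would be 43%.

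**6. Events left after a Day 720 landmark.** 1612 - 846 = 766, or 1612 - 802 = 810 with the longer range. Both are upper limits, because patients without a Day 720 sample drop out.

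**7. Can the bias be sized?** Not from the documents. As an illustration, assume no true treatment effect, the ANCHOR TG medians, a standard deviation of 30 points, responders defined by a fall of at least 20%, latent log-hazard SD of 0.3 to 0.5, and a correlation of 0 to 0.3 between that risk and marker change. About 47% of AMR101 and 19% of placebo patients are then responders. Simulated within-subgroup hazard ratios after a Day 120 or Day 720 landmark run from 0.98 to 1.09: close to 1 with no correlation, and above 1 (against the drug) with correlation. Other assumptions would give other results.

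**The case against.** **The method is inferred.** No section says outright how on-treatment change will be related to outcomes. Section 12.2.4.4 says only that event analyses will be similar to the secondary ones, and Sections 12.2 and 12.2.4.5 defer detail to a separate SAP. The text reviewed stops at the title page of Amendment 2. This limits the point: a landmark rule may exist elsewhere. It does not remove it, because the objective itself asks for the effect of therapy within the subgroup, and a landmark alone would not make that comparison randomised.

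**Section 9.2.3 does not ask for the same thing.** A reader might take its biomarker item as a second instance of the arm comparison. It describes an association between marker and outcome, which is legitimate if timed properly. This objection stands; only the Section 2 objective calls for the between-arm contrast.

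**Half of events is the worst case.** It applies to three markers of nine. A reader might also call all of those early events immortal time. Patients with nonfatal events stay in follow-up (Section 11.2), and an outcome event is not a valid reason to stop study drug (Section 11.1), so most can still be measured. Immortal time strictly concerns death or loss before the marker visit; for nonfatal events the problem is that the marker follows the outcome. This also stands.

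**Some patients may have an earlier sample.** Patients off drug for more than 30 days are asked to attend an interim visit with Visit 5 procedures (Section 11.1). That value is off treatment, so it does not help.

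**The objective is tertiary and unadjusted.** True. It limits the consequence but does not make the contrast valid.

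**Conclusion.** The concern holds for the Section 2 objective. Following it as written gives a non-randomised comparison for all nine markers. The timing problem is largest for apo B, hs-CRP and hsTnT (about 50% to 53% of first primary events before the first scheduled on-treatment value), intermediate for LDL-C as planned for analysis (about 27% of four-year events) and small for the other lipids (about 9%). These shares assume constant hazards at the plan's rates, uniform accrual, no dropout and the plan's stated follow-up.

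The shares count early events; they do not measure bias. A reader might infer that a mid-trial marker with half the events behind it must make the drug look much better. The documents do not support a size or a direction. A reader might also infer that this analysis is the planned basis for a claim about mechanism; no section gives it that role.

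The primary test, the key secondary test and the listed baseline subgroups are untouched. The change should be made, but it is not critical to the trial's main conclusion.

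**What to change.** 1. In the Section 2 objective (and the synopsis) and in the SAP, remove the between-arm comparison within subgroups defined by on-treatment marker change. Keep the randomised comparison of marker change and the subgroups defined by baseline values.
2. Keep the Section 9.2.3 marker-outcome association only as a landmark analysis, or as a Cox model with the marker as a time-dependent covariate. For the landmark version:
   - set time zero at the visit whose value is used: Day 120 for lipids other than LDL-C, Day 360 for ultracentrifugation LDL-C, Day 720 for apo B, hs-CRP and hsTnT;
   - include only patients free of the endpoint at the landmark and count only later events;
   - adjust for the baseline marker and the stratification factors.
3. Define what counts as a substantial change, or use the marker as a continuous variable. State how patients with no value at the landmark are handled.
4. Label the results as non-randomised associations.

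**Cost.** No new visits or samples. This is a wording change to a tertiary protocol objective as well as to the SAP, so the sponsor must decide under Section 21.1 whether it is a substantial amendment. The landmark analyses use fewer events: at most about 766 of 1612 after Day 720 with the shorter follow-up range, against about 1612 - 148 = 1464 after Day 120.

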3. STUDY DESIGN

3.1. Type of Study

Phase 3b, multi-Center, multinational, prospective, randomized, double-blind, placebo-controlled, parallel-group study

3.2. Study Population

The population for this study is men and women ≥ 45 years of age with established CVD, or men and women ≥ 50 years of age with diabetes in combination with one additional risk factor for CVD. In addition, all patients will have atherogenic dyslipidemia defined as on treatment for hypercholesterolemia (but at treatment goal for LDL-C, by treatment with a statin) and hypertriglyceridemia. More details are listed in the inclusion criteria.

The patients will need to provide consent to participate in the study and be willing and able to comply with the protocol and the study procedures.

3.3. Study Periods

This study consists of the following study periods:

- **Screening Period:** During the screening period, patients will be evaluated for inclusion/exclusion criteria.

At the first visit to the Research Unit (Visit 1), study procedures will be performed for evaluation of patient's eligibility in the study. At this screening visit, patients will sign an

informed consent form before any study procedure is performed; the informed consent form will cover the treatment/follow-up period. Based on the evaluation from Visit 1, the following situations may occur:

- Patients who are eligible for participation based on the study procedures on Visit 1 will return to the Research Unit for Visit 2 (randomization visit) to start the treatment/follow-up period. This case includes, for example, patients at Visit 1 who are on a stable dose of a statin, are planning to stay on the same statin and the same dose of the statin, and who not need to wash out any non-statin lipid-altering medications.
- Patients who are not eligible for participation based on the study procedures on Visit 1 and are unlikely to become eligible in the next 28 days (for example: unlikely to stabilize statin dose, unable to wash out non-statin lipid-altering medications, etc.): these patients will be screen failed after Visit 1.
- Patients not eligible for participation in the study based on the study procedures on Visit 1 may possibly become eligible in the next 28 days: these patients may return at the discretion of the investigator for a second optional screening visit (Visit 1.1) at which time the procedures needed for re-evaluation of the previously failed inclusion/exclusion criteria will be repeated. This case includes, for example, patients who are started on a statin at Visit 1, whose statin dose is changed at Visit 1, and/or needed to wash out non-statin lipid-altering medications. The following applies for these patients:
 - Patients with a change in the statin or statin dose on Visit 1 will need to be on a stable statin dose for at least 28 days before the lipid qualifying measurements at Visit 1.1. Other concomitant medications (antidiabetic therapy, for example) can be optimized or stabilized during this period.
 - Patients starting a washout at Visit 1 will have a washout period of at least 28 days (only 7 days for bile acid sequestrants) before the lipid qualifying measurements at Visit 1.1.
 - Patients at Visit 1 who are on a stable dose of a statin, are planning to stay on the same statin at the same dose, and who do not need any medication washout, but were asked to return for Visit 1.1 to repeat one or more of the other study procedures not related to concomitant medications
- Patients who become eligible for participation based on the additional study procedures at Visit 1.1 will return to the Research Unit for Visit 2 (randomization visit) to start the treatment/follow-up period.

At the end of the screening period, patients will need to meet all inclusion/exclusion criteria before they can be randomized. Patients who are not eligible for participation after the screening period (based on study procedures at Visit 1 and/or Visit 1.1) may return at a later date for rescreening. These patients will need to re-start with all procedures starting with Visit 1. This includes patients who need more time to stabilize one or more conditions or therapies (for example: statin, antidiabetic, antihypertensive, thyroid hormone, HIV-protease inhibitor therapy).

- **Treatment/Follow-Up Period:** Within 42 days after the first screening visit (Visit 1) or within 60 days after the first screening visit (Visit 1) for those patients that have a second

screening visit (Visit 1.1), eligible patients will enter the treatment/follow-up period. During this period, the patients will receive study drug during the planned visits at the Research Site and take the study drug while away from the Research Site.

During the visits, study procedures will be performed for evaluation of efficacy and safety. A detailed schedule of procedures is provided in Appendix A.

